9.3. Adverse Events

When calculating the incidence of adverse events (i.e., on a per subject basis), each subject will only be counted once per AE using the event with maximum severity and any repetitions of adverse events within a subject will be ignored; the denominator will be the total treatment group size or the corresponding number of subjects receiving the second dose, as appropriate. All unsolicited adverse events reported will be included in [Listing 11](#).

An overall summary of adverse events from first administration of study vaccine to the end of the study is presented in [Table 36](#), [Table 37](#), and [Table 38](#) for all subjects, baseline flavivirus positive subjects and baseline flavivirus negative subjects, respectively.

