Symptom		2.5 mcg ZPIV (N=X)	5 mcg ZPIV (N=X)	Placebo (N=X)	All Subjects (N=X)
Post Dose 1					
Any Local Reaction	n (%)	x (xx)	x (xx)	x (xx)	x (xx)
	95% CI	xx.x, xx.x	xx.x, xx.x	xx.x, xx.x	xx.x, xx.x
Repeat for:					
Pain					
Erythema					
Induration (mm)					
Induration					
Pruritis					
Ecchymosis					
Tenderness					
Any Systemic Reaction	n (%)	x (xx)	x (xx)	x (xx)	x (xx)
	95% CI	xx.x, xx.x	xx.x, xx.x	xx.x, xx.x	xx.x, xx.x
Repeat for:					
Feverishness					
Fatigue					
Malaise					
Myalgia					
Arthralgia					
Headache					
Nausea					
Vomiting					
Diarrhea					
Abdominal Pain					
Rash					
Fever					
Repeat for:					
Post Dose 2					
Post Any Dose					
Each event is defined as any grade 1, 2 or 3 solicited reaction within 7 days following either dose.					
N = Number of subjects in the safety population who received the specified dose; used as the denominator for percentages.					
n = Number of subjects reporting an event					

Tables with similar format:

Table 46: Number, Percentage and 95% Confidence Interval of Subjects Experiencing Any Grade 1 or Greater Solicited Adverse Event, by Dose, Symptom and Treatment Group – Baseline ZIKV Seropositive Subjects

[Implementation note: N = Number of subjects in the Safety population with the specified flavivirus immune status at baseline.]

Table 47: Number, Percentage and 95% Confidence Interval of Subjects Experiencing Any Grade 1 or Greater Solicited Adverse Event, by Dose, Symptom and Treatment Group – Baseline ZIKV Seronegative Subjects

[Implementation note: N = Number of subjects in the Safety population with the specified flavivirus immune status at baseline.]

Table 48: Number, Percentage and 95% Confidence Interval of Subjects Experiencing Any Grade 1 or Greater Solicited Adverse Event, by Dose, Symptom and Treatment Group – Baseline ZIKV Seropositive and DENV Seropositive Subjects

[Implementation note: N = Number of subjects in the Safety population with the specified flavivirus immune status at baseline.]

Table 49: Number, Percentage and 95% Confidence Interval of Subjects Experiencing Any Grade 1 or Greater Solicited Adverse Event, by Dose, Symptom and Treatment Group – Baseline ZIKV Seropositive and DENV Seronegative

[Implementation note: N = Number of subjects in the Safety population with the specified flavivirus immune status at baseline.]

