n = Number of subjects reporting an event							
For subjects receiving vaccinations in both arms, the maximum severity in either arm is summarized.							

Tables with similar format:

Table 60: Number and Percentage of Subjects Experiencing Solicited Systemic Events by Dose, Reaction, Severity, and Treatment Group – Baseline ZIKV Seropositive Subjects

[Implementation note: N = Number of subjects in the Safety population that were flavivirus seropositive at baseline.]

Table 61: Number and Percentage of Subjects Experiencing Solicited Systemic Events by Dose, Reaction, Severity, and Treatment Group – Baseline ZIKV Seronegative Subjects

[Implementation note: N = Number of subjects in the Safety population that were flavivirus seronegative at baseline.]

Table 62: Number and Percentage of Subjects Experiencing Solicited Systemic Events by Dose, Reaction, Severity, and Treatment Group – Baseline ZIKV Seropositive and DENV Seropositive Subjects

[Implementation note: N = Number of subjects in the Safety population that were flavivirus seropositive at baseline.]

Table 63: Number and Percentage of Subjects Experiencing Solicited Systemic Events by Dose, Reaction, Severity, and Treatment Group – Baseline ZIKV Seropositive and DENV Seronegative Subjects

[Implementation note: N = Number of subjects in the Safety population that were flavivirus seropositive at baseline.]

Table 64: Number and Percentage of Subjects Experiencing Solicited Systemic Events by Dose, Reaction, Severity, and Treatment Group – Baseline ZIKV Seronegative and DENV Seropositive Subjects

[Implementation note: N = Number of subjects in the Safety population that were flavivirus seropositive at baseline.]

Table 65: Number and Percentage of Subjects Experiencing Solicited Systemic Events by Dose, Reaction, Severity, and Treatment Group – Baseline ZIKV Seronegative and DENV Seronegative Subjects

[Implementation note: N = Number of subjects in the Safety population that were flavivirus seropositive at baseline.]

Table 66: Number and Percentage of Subjects Experiencing Solicited Local or Systemic Events by Symptom, Severity, and Day Post Dosing – 2.5 mcg ZPIV – Post Dose 1

2.5 mcg ZPIV, All subjects Dose Number = 1 (N=X)																				
Severity	Pre-Dose		30 mins Post-Dose		Day 1		Day 2		Day 3		Day 4		Day 5		Day 6		Day 7		Day 8+	
	n	%	n	%	n	%	n	%	n	%	n	%	n	%	n	%	n	%	n	%
Any Reaction																				
None	XX	XX	XX	XX	XX	XX	XX	XX	XX	XX	XX	XX	XX	XX	XX	XX	XX	XX	XX	

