[Implementation note: N = Number of subjects in the Safety population, dosage group, and baseline flavivirus immune status who received the specified dose.]

Table 125: Number and Percentage of Subjects Experiencing Solicited Local Events by Symptom, Severity, and Day Post Dosing – Baseline ZIKV Seronegative DENV Seronegative Subjects – 5 mcg ZPIV – Post Any Dose

[Implementation note: N = Number of subjects in the Safety population, dosage group, and baseline flavivirus immune status.]

Placebo**Table 126: Number and Percentage of Subjects Experiencing Solicited Local Events by Symptom, Severity, and Day Post Dosing – Baseline ZIKV Seronegative DENV Seronegative Subjects – Placebo – Post Dose 1**

[Implementation note: N = Number of subjects in the Safety population, dosage group, and baseline flavivirus immune status who received the specified dose.]

Table 127: Number and Percentage of Subjects Experiencing Solicited Local Events by Symptom, Severity, and Day Post Dosing – Baseline ZIKV Seronegative DENV Seronegative Subjects – Placebo – Post Dose 2

[Implementation note: N = Number of subjects in the Safety population, dosage group, and baseline flavivirus immune status who received the specified dose.]

Table 128: Number and Percentage of Subjects Experiencing Solicited Local Events by Symptom, Severity, and Day Post Dosing – Baseline ZIKV Seronegative DENV Seronegative Subjects – Placebo – Post Any Dose

[Implementation note: N = Number of subjects in the Safety population, dosage group, and baseline flavivirus immune status.]

14.3.1.2 Unsolicited Adverse Events**Table 129: Number and Percentage of Subjects Experiencing Unsolicited Adverse Events by MedDRA System Organ Class and Preferred Term, Severity, Relationship to Study Treatment, and Baseline Flavivirus Immune Status – 2.5 mcg ZPIV**

MedDRA System Organ Class	MedDRA Preferred Term	All subjects (N*=X)												Relationship to Treatment					
		Any Incidence			Severity						Not Related			Related					
					Mild			Moderate			Severe								
		n	%	m	n	%	m	n	%	m	n	%	m	n	%	m	n	%	m
Any SOC	Any PT	x	xx	x	x	xx	x	x	xx	x	x	xx	x	x	xx	x	x	xx	x
[SOC 1]	Any PT																		
	[PT 1]																		
	[PT 2]																		
[SOC 2]	Any PT																		
	[PT 1]																		
	[PT 2]																		
Repeat For:																			
Baseline ZIKV Seropositive																			
Baseline ZIKV Seronegative																			
Baseline ZIKV Seropositive and DENV Seropositive																			

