Baseline ZIKV Seronegative and DENV Seropositive (N* = X)															
Baseline ZIKV Seronegative and DENV Seronegative (N* = X)															

N = Number of subjects in the Safety Population who received the specified dose; N* = Number of subjects in the Safety population with the specified baseline flavivirus immune status, used as denominator for percentages; n=Number of subjects reporting an event under the SOC and PT combination; m = Number of events under the SOC and PT combination.

Post dose columns include events reported within 28 days following the dose; Post-Any Dose column includes events reported within 28 days following either dose.

95% CI = 95% exact Clopper-Pearson confidence interval

Tables with similar format:

Table 133: Number and Percentage of Subjects Experiencing Unsolicited Adverse Events by MedDRA System Organ Class, Preferred Term, Severity, Dose, and Baseline Flavivirus Immune Status – 5 mcg ZPIV

Table 134: Number and Percentage of Subjects Experiencing Unsolicited Adverse Events by MedDRA System Organ Class, Preferred Term, Severity, Dose, and Baseline Flavivirus Immune Status – Placebo

Table 135: Number and Percentage of Subjects Reporting NOCMCs by MedDRA System Organ Class, Preferred Term, Treatment Group, and Baseline Flavivirus Immune Status

Baseline Flavivirus Immune Status	MedDRA System Organ Class	MedDRA Preferred Term	2.5 mcg ZPIV (N=X)				5 mcg ZPIV (N=X)				Placebo (N=X)				All Subjects (N=X)			
			n	%	95 % CI	m	n	%	95 % CI	m	n	%	95 % CI	m	n	%	95 % CI	m
All Subjects (N* = X)	Any SOC	Any PT	x	xx	xx.x, xx.x	x	x	xx	xx.x, xx.x	x	x	xx	xx.x, xx.x	x	x	xx	xx.x, xx.x	x
	[SOC 1]	Any PT																
		[PT 1]																
		[PT 2]																
	[SOC 2]	Any PT																
		[PT 1]																
		[PT 2]																
Repeat for:																		
Baseline ZIKV Seropositive (N* = X)																		
Baseline ZIKV Seronegative (N* = X)																		
Baseline ZIKV Seropositive and DENV Seropositive (N* = X)																		
Baseline ZIKV Seropositive and DENV Seronegative (N* = X)																		
Baseline ZIKV Seronegative and DENV Seropositive (N* = X)																		
Baseline ZIKV Seronegative and DENV Seronegative (N* = X)																		

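### Post-Dose 2 percentages in SAP Tables 132-134, and by their notes in Tables 46-51, 53-58 and 60-65, are set on the whole serostatus stratum instead of dose-2 recipients, against SAP 9.3

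*SAP*

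**What the plan says.** **General rule.** For the per-subject incidence of adverse events, SAP 9.3 states that "the denominator will be the total treatment group size or the corresponding number of subjects receiving the second dose, as appropriate".

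**Unsolicited events by dose (Tables 132-134).** The Table 132 footnote defines two counts. One is dose-specific and heads each column: "N = Number of subjects in the Safety Population who received the specified dose". The other is the stratum count, given once per row block: "N* = Number of subjects in the Safety population with the specified baseline flavivirus immune status, used as denominator for percentages". The numerator depends on the dose: "Post dose columns include events reported within 28 days following the dose".

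**Solicited events by dose.** Table 45 (all subjects) uses "N = Number of subjects in the safety population who received the specified dose; used as the denominator for percentages". Tables 52 and 59, also for all subjects, define N by receipt of the dose. The serostatus versions carry their own notes. For Tables 46-51 and 53-58 the note is "N = Number of subjects in the Safety population with the specified flavivirus immune status at baseline". For Tables 60 and 62-65 it is "N = Number of subjects in the Safety population that were flavivirus seropositive at baseline", and Table 61 has the seronegative equivalent. None of these notes mentions receipt of a dose, although the tables repeat for Post Dose 2.

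**Tables that keep the dose condition.** In the Post Dose 1 and Post Dose 2 versions of the by-day serostatus tables (75-128) the note is "N = Number of subjects in the Safety population, dosage group, and baseline flavivirus immune status who received the specified dose". Table 44 defines N as those who received the dose in question, and Table 43 has a count row on that basis.

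**The concern.** The Safety population requires only one study vaccination (SAP 6.3.1). Subjects who do not get the boost are asked to stay in follow-up (Protocol 5.3.3), and SAP 7.1 plans a comparison of those who miss it. A stratum can therefore contain subjects who were never at risk of a post-boost event. Dividing by the whole stratum counts them as event-free after an injection they did not receive, which can only pull the rate down.

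Some of these subjects are not boosted because of what happened after dose 1 (Protocol 9.5.2), and the share missing dose 2 may differ between arms. The dilution need not then be equal across the columns being compared. At stake are the by-dose, by-serostatus displays for primary endpoint 1 (solicited reactogenicity after each administration) and the by-dose tables of unsolicited events. A reader comparing Table 46 with Table 44 or with Tables 75-83 could find post-dose-2 percentages for the same stratum on different bases, with nothing to explain why.

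**Working it through.** **Which denominator each table uses for Post-Dose 2**

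| SAP tables | Content | Denominator as written |
|---|---|---|
| 45, 52, 59 | Solicited, all subjects | Received the dose |
| 44, and count row of 43 | Solicited, with serostatus panels | Received the dose |
| 75-128, post-dose versions | Solicited by day, by serostatus | Stratum members who received the dose |
| 46-51, 53-58, 60-65 | Solicited by serostatus | Stratum, no dose condition |
| 132-134 | Unsolicited by dose, all-subjects block and strata | Stratum (N*), no dose condition |

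The last two rows depart from SAP 9.3 and from the first three. Post-Dose 1 and Post-Any-Dose entries are not affected, because every Safety subject received at least one vaccination.

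**Size of the error.** Let x be the subjects with an event after dose 2, N* the stratum size and N2 the number in it who received dose 2.

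- Shown rate = x/N*; correct rate = x/N2.
- Shown/correct = N2/N*, that is, 1 minus the share who missed dose 2.

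The ratio cannot exceed 1, and equals 1 when N2 = N*.

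**Inputs.** Planned arm sizes are 45 (5 mcg), 35 (2.5 mcg) and 5 + 5 = 10 pooled placebo (SAP 4.4.3). The documents give no number for missed second doses, no event counts and no stratum sizes, so those below are assumptions. There is no figure in the plan to reproduce. Intervals are 95% Clopper-Pearson.

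| Assumed case | As written | On dose-2 recipients | Shown/correct |
|---|---|---|---|
| 5 mcg, none missed, 10 events | 10/45 = 22.2% (11.2-37.1) | the same | 1.00 |
| 5 mcg, 3 missed, 10 events | 10/45 = 22.2% (11.2-37.1) | 10/42 = 23.8% (12.1-39.5) | 42/45 = 0.93 |
| 5 mcg, 7 missed, 10 events | 10/45 = 22.2% (11.2-37.1) | 10/38 = 26.3% (13.4-43.1) | 38/45 = 0.84 |
| 2.5 mcg, 2 missed, 7 events | 7/35 = 20.0% (8.4-36.9) | 7/33 = 21.2% (9.0-38.9) | 33/35 = 0.94 |
| Placebo, 2 missed, 2 events | 2/10 = 20.0% (2.5-55.6) | 2/8 = 25.0% (3.2-65.1) | 8/10 = 0.80 |
| Stratum of 8, 2 missed, 1 event | 1/8 = 12.5% (0.3-52.7) | 1/6 = 16.7% (0.4-64.1) | 6/8 = 0.75 |

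**Stratum named in the notes.** Table 65 covers subjects seronegative for both ZIKV and DENV, yet its note says flavivirus seropositive, which is the opposite group. The notes to Tables 62-64 use the same general term for three different ZIKV/DENV combinations, so they do not identify the titled stratum.

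**The case against.** The strongest reply is that SAP 9.3 governs. Tables 46-51 and 53-58 are introduced as having a similar format to parents that require receipt of the dose, so their notes may only add the stratum restriction. That reading is possible. But the notes to Tables 75-128 state the dose condition for each single dose and omit it only for Post Any Dose, so in these shells the wording carries meaning. The reply does not help Tables 132-134, where the footnote defines the dose-specific count and then assigns the percentages to the other one.

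It is also fair that the effect may be small: with 42 of 45 boosted the intervals barely move. The Table 132 header shows the dose-2 count, so the all-subjects rate can be recomputed. The strata cannot be, because only N* is given for them.

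Several stronger readings are tempting but unsupported:

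- A reader might infer that every serostatus table is affected. Tables 43, 44 and 75-128 condition on dose, and Table 52, an all-subjects table, is already right.
- A reader might infer that primary endpoint 2 is misreported. That endpoint is cumulative and concerns vaccine-related events; Tables 36-42 and 129-131 report it, and there the full stratum is the proper denominator.
- A reader might infer that p-values change. The Table 43 comparisons rest on dose-recipient counts.
- A reader might take Table 64 to name the opposite stratum. It is DENV seropositive, so its note is only imprecise.
- A reader might infer that the correction removes selection. It does not: dose-2 recipients are partly selected for having tolerated dose 1, and Protocol 9.5.2 also lists reasons unrelated to reactions.

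**Conclusion.** The point holds for Tables 132-134 and for the notes to Tables 46-51, 53-58 and 60-65. As written, their Post-Dose 2 percentages use a denominator that conflicts with SAP 9.3 and with the SAP's other tables for the same strata. The evidence is clearest for Tables 132-134.

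The direction is known: never upward, and zero if every subject in the stratum is boosted. The size is not known. An error of about 7% to 16% of the correct rate follows only from assuming that 3 to 7 of 45 miss dose 2; in placebo or small strata one or two missed boosts can do more. That the exact intervals share the denominator is the natural reading of the footnote, which mentions only percentages. Severity is minor: the displays are descriptive and no planned test is shown to change.

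**What to change.** 1. In the Post-Dose 2 columns or sections of Tables 132-134, 46-51, 53-58 and 60-65, set the denominator for percentages and exact intervals to Safety subjects in the titled stratum and treatment group who received dose 2. Keep the full stratum for Post-Dose 1 and Post-Any-Dose.
2. In Tables 132-134, show that dose-2 count for each stratum block so that every percentage can be checked.
3. Correct the Table 65 note to the double-seronegative stratum, and make the notes to Tables 62-64 name the stratum in the title. Leave Table 52 as it is.

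The cost is edits to shell notes and the matching denominators in the table programs. No new data, endpoint or method is needed.

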13. Subject has a fever (defined as an oral temperature  $\geq 38.0^{\circ}\text{C}$ ) or a moderate or severe acute illness at the time of boost vaccination administration or in the 2 days prior to Day 29. The 2nd study vaccination can be deferred until the fever or illness resolves or only minor residual symptoms remain, that in the opinion of the investigator, will not interfere with the ability to assess safety parameters as required by the protocol, provided that the boost is given within the protocol-defined study window. Permission to give the 2nd study vaccination outside the protocol-defined study window must be obtained from DMID.

Note: in case the boost vaccination is postponed, the timing of the safety/immunogenicity visits post-boost will be planned relative to actual vaccination day.

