3.2. Endpoints

Primary Endpoints:

1. Frequency and severity of solicited injection site and systemic reactogenicity from time of study vaccine administration through Day 8 after each administration of study vaccine overall and by dosage group and pre-vaccination flavivirus immune status.
2. Frequency and severity of unsolicited vaccine-related adverse events (AE), including vaccine-related laboratory AE, from first administration of study vaccine until 28 days after the last vaccination overall and by dosage group and pre-vaccination flavivirus immune status.
3. Frequency, type, and duration of serious adverse events (SAE) and adverse events of special interest (AESI) considered related to study vaccine from the first administration of study vaccine until the end of the study overall, and by dosage group and pre-vaccination flavivirus immune status.
4. Frequency of new onset chronic medical conditions reported at any time from the first administration of study vaccine until the end of the study overall, and by dosage group and pre-vaccination flavivirus immune status.
5. Comparison of the frequency, type and duration of vaccine-related Grade 3 local, systemic, or laboratory AE, and Grade 2 or greater local or systemic reactogenicity through Day 8 after each

study vaccine administration between dosage groups and by pre-vaccination flavivirus immune status.

6. Comparison of study withdrawals and discontinuation of study vaccination due to any reason between dosage groups and by pre-vaccination flavivirus immune status.

Secondary Endpoints:

1. Frequency of seroconversion to ZIKV at each post-vaccination visit measured by ZIKV ELISA and neutralization assay in comparison with baseline samples (collected at Visit 00) overall, and by dosage group and pre-vaccination flavivirus immune status.
2. Per Visit GMT as measured by ZIKV ELISA and neutralization assay after each study vaccine administration and for each post-vaccination visit overall, and by dosage group and pre-vaccination flavivirus immune status.
3. Peak GMT as measured by ZIKV ELISA and neutralization assay after each vaccination and overall, and by dosage group and pre-vaccination flavivirus immune status.
4. Proportion of subjects with at least a 4-fold rise in ZIKV GMT as measured by ZIKV ELISA and neutralization assay at 4 weeks after each vaccination compared with baseline overall, and by dosage group and pre-vaccination flavivirus immune status.

Exploratory Endpoints:

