9.3.2. Unsolicited Adverse Events

The frequency of all unsolicited AEs reported per subject from first administration of study vaccine to 28 days after the last vaccination are presented by MedDRA SOC, PT, severity, relationship to study treatment, and baseline flavivirus status in [Table 129](#) (2.5 mcg ZPIV), [Table 130](#) (5 mcg ZPIV), and [Table 131](#) (placebo).

The frequency of all unsolicited AEs reported per subject from first administration of study vaccine to 28 days after the last vaccination are presented in the following tables by MedDRA SOC, PT, severity, dose, and baseline flavivirus status in [Table 132](#) (2.5 mcg ZPIV), [Table 133](#) (5 mcg ZPIV), and [Table 134](#) (placebo).

[Figure 58](#), [Figure 59](#), and [Figure 60](#) are graphical representations of the number and severity of all unsolicited adverse events overall and by treatment group and MedDRA SOC following any dose, post dose 1, and post dose 2, respectively. Similar presentations for adverse events determined to be related to study product are available in [Figure 61](#), [Figure 62](#), and [Figure 63](#).

Refer to [Listing 11](#) for a detailed listing of all unsolicited adverse events. [Table 189](#) includes a listing of all serious adverse events and [Table 190](#) includes a listing of all non-serious unsolicited moderate or severe adverse events.

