14.3 Safety Data

14.3.1 Displays of Adverse Events

Table 36: Overall Summary of Adverse Events – All Subjects

Event Category ^a	Subcategory	2.5 mcg ZPIV (N=X)		5 mcg ZPIV (N=X)		Placebo (N=X)		All Subjects (N=X)	
		n (%)	95% CI	n (%)	95% CI	n (%)	95% CI	n (%)	95% CI
At least one local solicited adverse event ^b		xx (xx)	xx.x, xx.x	xx (xx)	xx.x, xx.x	xx (xx)	xx.x, xx.x	xx (xx)	xx.x, xx.x
At least one systemic solicited adverse event ^b									
At least one unsolicited adverse event ^c									
At least one related unsolicited adverse event ^c	Any Severity								
	Mild (Grade 1)								
	Moderate (Grade 2)								
	Severe (Grade 3)								
At least one related laboratory adverse event ^c	Any Severity								
	Mild (Grade 1)								
	Moderate (Grade 2)								
	Severe (Grade 3)								
	Any Severity								
At least one related unsolicited or laboratory adverse event ^c	Mild (Grade 1)								
	Moderate (Grade 2)								
	Severe (Grade 3)								
	Any Relationship								
	Related								
At least one severe (Grade 3) unsolicited adverse event ^c	Unrelated								
At least one serious adverse event ^d									
At least one related serious adverse event ^d									
At least one adverse event leading to early termination from the study ^d									

Table 36: Overall Summary of Adverse Events -- All Subjects (continued)

Event Category ^a	Subcategory	2.5 mcg ZPIV (N=X)		5 mcg ZPIV (N=X)		Placebo (N=X)		All Subjects (N=X)	
		n (%)	95% CI	n (%)	95% CI	n (%)	95% CI	n (%)	95% CI
At least one adverse event leading to discontinuation of study product									
At least one adverse event of special interest (AESI) ^d									
At least one related AESI ^d									
At least one new onset chronic medical condition (NOCMC) ^d									
At least one related NOCMC ^d									

N = Number of subjects in the safety population. CI = Exact (Clopper-Pearson) confidence interval.
n = Number of subjects experiencing the event.

^a Subjects are counted once for each category regardless of the number of events.
^b Solicited AEs are collected through Day 8 post each dose.
^c Non-serious unsolicited AEs within 28 days of either dose.
^d At any time during the study.

Tables with similar format:

Table 37: Overall Summary of Adverse Events – Baseline ZIKV Seropositive Subjects

[Implementation note: N = Number of subjects in the Safety population with specified baseline flavivirus immune status]

Table 38: Overall Summary of Adverse Events – Baseline ZIKV Seronegative Subjects

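### Tables 36-42 and the Post-Any Dose column of Tables 132-134 count unsolicited AEs in two separate 28-day windows, whereas primary endpoint 2 sets one continuous period, so events before a late boost drop out

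*SAP*

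**What the plan says.** SAP 3.2 sets the period for primary endpoint 2: "from first administration of study vaccine until 28 days after the last vaccination". SAP 9.3.2 uses the same period for Tables 129-131, and again for Tables 132-134, where it covers all unsolicited AEs "reported per subject from first administration of study vaccine to 28 days after the last vaccination are presented in the following tables". The Table 129 footnote agrees with it.

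The mock-ups in SAP Appendix 1 depart from this in two places:

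- **Table 132 footnote (Tables 132-134).** For the single-dose columns: "Post dose columns include events reported within 28 days following the dose". For the combined column: "Post-Any Dose column includes events reported within 28 days following either dose".
- **Table 36 footnote c.** The unsolicited and laboratory AE rows are defined as "Non-serious unsolicited AEs within 28 days of either dose". Tables 37-42 share the format.

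SAP 9.3 adds a third definition. It describes Tables 36-38 as running from the first vaccination to the end of the study.

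SAP 4.4.5 schedules the second dose for Day 29 ± 3. Protocol 9.5.2, item 13, foresees a later one: permission to give it "outside the protocol-defined study window must be obtained from DMID". No latest day is stated.

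**The concern.** The union of two 28-day windows equals the endpoint's period only if the second window opens before, or as soon as, the first one closes. When the boost is later than that, some days belong to the endpoint's period but to neither window. An AE starting on those days would be absent from the overall AE summary and from the Post-Any Dose column, yet present in Tables 129-131. The report could then give two totals for one primary safety endpoint, and a programmer could not satisfy both SAP 9.3.2 and the footnote of the tables it describes.

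The affected tables matter. Protocol 11.4.2 asks for exact 95% confidence intervals for related unsolicited AEs, by group and for each vaccination. The Table 129 shell has neither an interval nor a split by dose. Among the unsolicited-AE summary tables, intervals appear in Tables 36-42 and 132-134, and the dose split only in Tables 132-134. These are the tables that carry the two-window rule.

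**Working it through.** **Inputs.** Dose 1 is on Day 1. The boost is on Day b, with b from 26 to 32 in window (SAP 4.4.5) or later with permission (Protocol 9.5.2). Each window is 28 days (Table 36 and Table 132 footnotes). An AE is placed by its onset day.

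**The plan's own figure.** SAP 4.5 ends unsolicited AE collection on Day 57 for an on-schedule boost: 29 + 28 = 57. This reproduces, so 28 days after Day 1 is taken as Day 29.

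**Definitions.**
- Dose 1 window: Days 1 to 29.
- Dose 2 window: Days b to b + 28.
- Endpoint period: Days 1 to b + 28.
- Gap, in the endpoint period but in neither window: Days 30 to b − 1, which is max(0, b − 30) days.
- Overlap of the two windows: Days b to 29, which is max(0, 30 − b) days.

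| Boost day b | Gap (days) | Endpoint period (days) | Gap share | Overlap (days) |
|---|---|---|---|---|
| 26 | 0 | 54 | 0% | 4 |
| 27 | 0 | 55 | 0% | 3 |
| 28 | 0 | 56 | 0% | 2 |
| 29 | 0 | 57 | 0% | 1 |
| 30 | 0 | 58 | 0% | 0 |
| 31 | 1 | 59 | 1.7% | 0 |
| 32 | 2 | 60 | 3.3% | 0 |
| 36 (assumed) | 6 | 64 | 9.4% | 0 |
| 43 (assumed) | 13 | 71 | 18.3% | 0 |
| 57 (assumed) | 27 | 85 | 31.8% | 0 |

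The last three rows only illustrate the formula; the documents give no actual boost dates.

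**Stricter reading.** If 28 days means Days 1 to 28, the gap becomes max(0, b − 29). That is 1 day for Day 30, 2 for Day 31 and 3 for Day 32. The overlap shrinks by one day and disappears for an on-schedule boost.

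**Where the overlap shows.** Tables 36-42 have no dose columns, and footnote a of Table 36 counts a subject once per category. The Post-Any Dose column is a union, so an event in both windows enters it once. Overlap can therefore only place one event in both the Post-Dose 1 and Post-Dose 2 columns of Tables 132-134, when the boost is on or before Day 29.

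**Weight of one subject.** SAP 4.4.3 plans 35 subjects on 2.5 mcg, 45 on 5 mcg and 5 + 5 = 10 on placebo. One subject missed changes an arm's rate by 1/35 = 2.9, 1/45 = 2.2 or 1/10 = 10 percentage points.

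**After the change.** With the endpoint's period, Days 1 to b + 28, the gap is 0 for every b.

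**The case against.** The strongest reply is that this is a conflict between table footnotes and body text that is already right, and that no event vanishes from the report. Much of that stands. SAP 9.3.2 states the correct period for Tables 132-134. Tables 129-131 give frequency, severity and relationship over the full period. Listing 11 holds every unsolicited AE. For an in-window boost the gap is at most 2 days, or 3 on the stricter reading. None of this settles which rule is programmed for Tables 36-42 and 132-134, and Tables 129-131 cannot supply the intervals or the dose split.

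A reader might also infer that the loss is systematic, because an AE can itself delay the boost. The documents give this little support. Protocol 9.5.2, item 8, requires a Grade 2 or greater AE to settle within the vaccination window, so that deferral ends by Day 32. The provision for going outside the window sits in item 13, on fever and acute illness. An AE that defers a Day 29 boost will usually have begun by Day 29, inside the dose 1 window, and is counted. Only a further AE starting from Day 30 up to the day before the boost is missed.

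Another tempting inference is that the headline tables count events twice; the working shows that they do not. Even the repeat across the two dose columns is not certain, because Listing 11 ties each event to a single dose number. The SAP does not say whether that field drives the columns.

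**Conclusion.** The two footnotes are wrong as written against primary endpoint 2, and the Table 132 footnote also contradicts the SAP text for its own tables. The consequence is an undercount in the footnote c rows of Tables 36-42 and in the Post-Any Dose column, and possible disagreement with Tables 129-131. It is confined to subjects boosted after Day 30: 1 to 2 days of follow-up for an in-window boost on Day 31 or 32, and more for a later permitted one. Subjects boosted out of window leave the per-protocol set (SAP 6.3.3) but remain in the Safety population (SAP 6.3.1), so they do enter these tables.

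The result assumes that 28 days after Day 1 is Day 29 and that events are placed by onset. How many subjects were boosted late is unknown, so a gap of two weeks or more is an illustration and not an expected loss. Nor is the primary endpoint itself lost, since Tables 129-131 still report it over the right period. The correction is worth making because the rule gives wrong counts in the tables that carry the intervals, and it is nearly free.

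**What to change.** 1. In footnote c of Table 36 (and so Tables 37-42) and in the Post-Any Dose definition of Tables 132-134, state the period as first vaccination through 28 days after the last vaccination received.
2. Amend the SAP 9.3 sentence so that the unsolicited and laboratory AE rows of the overall summary use this period. Keep the end-of-study period for the rows that footnote d already assigns to it.
3. Optionally, assign an event that falls in both dose windows to one dose column, for example by the dose-number field in Listing 11, and say so in the Table 132 footnote.

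The 28-day windows for the Post-Dose 1 and Post-Dose 2 columns can stay. Running Post-Dose 1 up to the boost would leave no event without a dose column, but it gives up equal windows: with a Day 57 boost it would last 56 days against 29 for Days 57 to 85. If the equal windows are kept, add a note that an event between them appears in the Post-Any Dose column only.

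The cost is two footnotes, one sentence and the matching derivation. Protocol 9.4 already collects unsolicited AEs through about 28 days after the last vaccination, so no further data are needed.
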